IMPACT OF HEAD OF BED ELEVATION IN SYMPTOMS OF PATIENTS WITH GASTROESOPHAGEAL REFLUX DISEASE: A RANDOMIZED SINGLE-BLIND STUDY (IBELGA)

INTERNAL MEDICINE POSTGRADUATE THESIS PROTOCOL

MENTOR: [name] RESIDENT: [name] RESIDENT: [name]

> BOGOTÁ D.C. MARCH 2ND, 2017

EXECUTIVE SUMMARY

Background: Gastroesophageal reflux disease is a very frequent clinical condition and nocturnal symptoms are a cause of quality of life impairment, poor sleep quality and absenteeism. Because of factors such as a prolonged acid exposure during sleep, nocturnal reflux has been associated to esophagitis, more extra-esophageal symptoms and other illnesses such as asthma. Head of bed elevation, as a low-cost non pharmacologic anti-reflux treatment is nowadays recommended, but its clinical impact in patients with nocturnal symptoms remains unknown due to inconsistent results and methodological limitations among different clinical trials, most of which were performed before the widespread use of proton pump inhibitors in clinical practice.

Hypothesis: Head of bed elevation is a useful treatment for patients with gastroesophageal reflux disease and nocturnal symptoms, and has a positive impact in quality of life in these patients.

Study Objective: To assess the effectiveness of head of bed elevation for treatment of patients with gastroesophageal reflux disease and nocturnal symptoms, and to determine the impact of this intervention in quality of life of these patients.

Methods: Randomized single-blind single-centre controlled clinical trial with a 2x2 cross-over design. A sample of 42 patients attending to the outpatient gastroenterology unit at Clínica Fundadores in Bogotá city, who meet the inclusion criteria and have no exclusion criteria will be selected to participate. Included patients will be randomized to raise the head of bed with standard 20 cm-height wooden blocks or to sleep without bed inclination during the first 6 week period. After a 2 week washout period, allocation will be crossed and participants will be followed again during a second 6 week period. During the trial, every patient will receive standard pharmacological treatment with a proton pump inhibitor and/or sodium alginate and the researchers in charge of statistical analysis and reporting results will be blinded for the non pharmacological intervention under study. Primary outcome is a significant symptom reduction according to RDQ validated questionnaire and secondary outcomes include quality of life impact according to SF-36 validated questionnaire, patient preference and adverse events of non pharmacological intervention. Statistical analysis will be carried out with STATA 13.0 (Special Edition) statistical package for Windows. Differences with a p<0,05 will be accepted as statistically significant.

Expected results: Effectiveness of head of bed elevation in the treatment of patients with symptomatic nocturnal gastroesophageal reflux disease will be assessed. New knowledge for generation of a local and international recommendation about non pharmacological treatment of gastroesophageal reflux disease will be provided. Colombian researchers will be trained in methodological aspects concerning design, conduction and analysis of clinical trials in this field of medical knowledge.

Keywords: Gastroesophageal reflux disease, head of bed elevation, lifestyle measures, nocturnal symptoms, quality of life.

PROBLEM STATEMENT

Gastroesophageal reflux disease (GERD) is a clinical condition characterized by troublesome symptoms and medical complications as a result of reflux of gastric contents into the esophagus¹. GERD is diagnosed in 4% of primary care outpatient visits² and the disease prevalence in Latin-America reaches 12-31%³. Nocturnal symptoms have been found in 74% of patients with GERD and are a cause of significant quality of life impairment, when compared with general population and

patients with GERD and daytime-only symptoms⁴. Sleep interference secondary to nocturnal retrosternal burning has been associated to lower work productivity⁵, even in patients being treated with proton pump inhibitors (PPI)⁶. Due to several physiological factors such as lack of conscious perception of symptoms, reduced salivation and a lower frequency of nocturnal swallowing⁷, a significantly longer acid exposure overnight has been associated to the emergence of complications like esophagitis^{8, 9}, more extra-esophageal symptoms¹⁰ and other illnesses such as asthma¹¹.

As a low-cost non pharmacological anti-reflux treatment for GERD, head of bed elevation (HBE) is nowadays moderate-strength recommendation with a low level of evidence¹²⁻¹⁵. Clinical impact of this measure in patients with night-time symptoms remains unknown, due to inconsistent results and methodological limitations among different clinical trials; most of which were performed before the widespread use of proton pump inhibitors in clinical practice. Evidence from several non-randomized studies suggest that HBE could reduce esophageal acid exposure time and could decrease GERD symptoms¹⁶⁻¹⁸; however, another study found no significant differences in those same outcomes¹⁹. On the other hand, all randomized controlled clinical trials published this far show inconsistent results. A study published before widely accepted clinical use of PPI, revealed significant clinical and endoscopic improvement in patients with GERD and grade C-D esophagitis allocated to receive HBE, when compared with controls²⁰. In contrast, a multi-centre clinical trial found no difference in symptom score or antacid use among groups allocated to HBE and control group²¹. All cited studies have methodological limitations and heterogeneity in outcome assessments, which makes difficult conducting a meta-analysis with these data^{22, 23}. No published studies evaluating impact of HBE in quality of life or work productivity were found. Table 1 summarizes published evidence to date.

Study [Population]	Jadad score	Follow-up	n	Major findings	Main limitation	Reference
Stanciu C, 1977 [GERD]	1	15 hours	63	↓ acid exposure time, clinical improvement	Non-randomized Short follow-up	16
Johnson L, 1981 [GERD]	0	ND	55	↓ acid exposure time	Non-randomized No symptom assessment	17
Harvey R, 1987 [C/D Esophagitis]	3	6 weeks	71	Clinical and endoscopic improvement	Pre-PPI era	20
Hamilton J, 1988 [Esophagitis]	3	3 days	15	No acid exposure time reduction nor clinical improvement	Low power Short follow-up	19
Pollmann H, 1996 [GERD]	NA	2 weeks	NA	No clinical improvement	Full text unavailable Non-structured abstract	21
Khan BA, 2012 [Nocturnal GERD]	1	1 week	20	↓ acid exposure time, clinical improvement	Non-randomized Inpatient setting	18

Table 1: Summary of HBE clinical trials in GERD published to date. NA: Unavailable; PPI: proton pump inhibitor; ↓: reduction

HYPOTHESIS

Head of bed elevation is a useful treatment for patients with GERD and nocturnal symptoms, and has a positive impact in quality of life in these patients.

STUDY OBJECTIVES

General Objective: To assess the effectiveness of HBE for treatment of patients with GERD and nocturnal symptoms, and to determine the impact of this intervention in quality of life of these patients.

Specific Objectives:

- 1. To identify, recruit and randomize participants with strict allocation concealment.
- 2. To compare symptom severity and quality of life among participants allocated to the HBE and the control group, in both the first and second period of study.
- 3. To assess therapeutic adherence and adverse event occurrence periodically by means of telephone call and photographic documentation of patient compliance with assigned intervention.

PATIENTS AND METHODS

General design: Randomized single-blind single-centre controlled clinical trial with a 2x2 cross-over design, in a sample of patients attending to the outpatient visit at the Gastroenterology, Digestive endoscopy and Liver Diseases Unit in Clínica Fundadores, Bogotá city. Participants who meet the inclusion and have no exclusion criteria will be randomized to raise the head of bed with standard 20 cm-height wooden blocks or to sleep without bed inclination during 2 periods of 6 weeks each, separated by a washout 2 week period. During the trial, every patient will receive standard pharmacological treatment with a proton pump inhibitor and/or sodium alginate, according to treating physician criteria, and the researchers in charge of statistical analysis and reporting results will be blinded for the non pharmacological intervention under study. Primary outcome is a significant symptom reduction according to RDQ validated questionnaire and secondary outcomes include quality of life impact according to SF-36 validated questionnaire, patient preference and adverse events of non pharmacological intervention.

The trial will be conducted during 8 months and will be divided into 4 successive stages.

- 1. Stage I: 2 months during which the first 4 specific objectives will be accomplished.
- 2. Stage II: 4 months for specific objectives 5 to 7.
- 3. Stage III: 1 month for specific objective 8 and results discussion.
- 4. Stage IV: 1 month for specific objectives 9 and 10.

In figure 1 and table 2, different stages with respective component activities are outlined.

[figure not shown]

Figure 1: Clinical trial stages

Patient recruitment: Because of a low recruitment rate, an active participant search system was finally implemented. This system was based on telephone calls, using a database with patient data from all upper gastrointestinal endoscopies performed in the Gastroenterology Unit at Clínica Fundadores in Bogotá city, between years 2014 to 2016. Patients were pre-selected based on endoscopically diagnosed erosive esophagitis of any grade, which is one of the clinical trial inclusion criteria. In order to minimize selection bias, 2 interviewers performed telephone calls in a consecutive chronologic order to all patients in the database without exception. In all cases, the same standardized telephone call format was used.

Sample size: Null hypothesis (H_0) and unidirectional alternative hypothesis (H_1) of the trial are represented below:

$$H_0$$
: RDQ_{HBE}= RDQ_{NoHBE} H_1 : RDQ_{HBE}< RDQ_{NoHBE} H_0 : SF-36_{HBE}= SF-36_{NoHBE} H_1 : SF-36_{HBE}> SF-36_{NoHBE}

Sample size was estimated based on the hypothesis that HBE would produce a difference of at least 10% in RDQ and SF-36 scores. Effect size (Cohen d) was calculated as 0,49 keeping in mind an RDQ mean and standard deviation of 3,3±1,0 previously found in Spanish population with symptomatic GERD²⁴ and an SF-36 mean and standard deviation of 56,9±20,3 reported in Italian population in medical therapy with PPI²⁵. The minimally important difference selection was chosen based on the assumption that any difference smaller than 10% would have no clinical relevance. Based on this data, 14 patients per group would yield a power greater than 80% for detection of a minimally important difference as large as or larger than 0,6 points in RDQ questionnaire (range: 1 to 6) and 10 points in SF-36 questionnaire (range: 0 to 100), when using a paired t test as described in the statistical analyses plan section. Because of a complementary analysis of crossover data is planned with McNemar marginal homogeneity test, effect size was recalculated based on results of a previous trial²⁰, according to which, 58,8 % and 28,6% of placebo-treated patients in pre-omeprazole era, reported improvement of GERD symptoms with and without a HBE of 20 cm, respectively. Based on these data, and maintaining a statistical power of 80%, required sample size was adjusted to a total of 34 patients. In

figure 2, matrices for sample size calculation are shown, based on the cited trial and using internationally accepted statistical procedures²⁶. Likewise, in table 3 an output of sample size calculation is shown from G*Power 3.1.9.2 (Universität Düsseldorf, Düseldorf, Germany) software²⁷. Finally, calculated sample size was increased by 20% in order to avoid study power loss due to drop-outs or losses of follow-up. Thus, final sample size was 42 patients, 21 per group.

T test	Means: Difference between two dependent means	(matched pairs)
Analysis	A priori: Compute required sample size	
Input	Tails	One
	Effect size dz	0,4926108
	A err prob	0,05
	Power (1- β err prob)	0,8
Output	Noncentrality parameter δ	2,5596808
	Critical t	1,7056179
	Degrees of freedom	26
	Total sample size	27
	Actual power	0,8015888
McNemar	Proportions: Inequality, two dependent groups	
Analysis	A priori: Compute required sample size	
Input	Tails	One
	Odds ratio	3,571
	α	0,05
	1- β	0,8
	Prop discordant pairs	0,53782
Output	Lower critical N	13,0000000
	Upper critical N	13,0000000
	Total sample size	34
	Actual power	0,8169370
	Actual α	0,0481262
	Proportion p12	0,4201608
	Proportion p21	0,1176592

Table 3: Sample size calculation output with G*Power 3.1.9.2 software²⁷

Inclusion criteria:

Patients with GERD who meet with all the following characteristics:

- 1. Diagnosis of GERD based on Montreal definition (Esophageal erosions and typical symptoms such as pyrosis and/or regurgitation with a frequency ≥ 2 times per week).
- 2. Retrosternal pyrosis lasting ≥ 3 months.
- 3. Pyrosis and/or regurgitation with a frequency ≥ 3 nights per week
- **4.** GERD-associated sleep disturbance (insomnia, poor sleep quality) with a frequency ≥ 3 nights per week, and lasting ≥ 1 month.

Exclusion criteria: Patients with atypical symptoms and no erosions on endoscopy (NERD: Non-erosive Gastroesophageal Reflux Disease) will not be included. Likewise, patients with the following situations will be excluded from the trial: peptic ulcer, history of biliary surgery, lactating or pregnant women, participants under 18 years of age and nighttime shift workers (12 am to 6 am). Patients with the following conditions which affect sleep quality will also be excluded: Obstructive sleep apnea

hypopnea syndrome, chronic obstructive pulmonary disease, patients with nocturnal supplementary oxygen requirement, orthopnea, nocturia, restless legs syndrome, patients consuming more than 3 cups of coffee per day, patients planning to travel beyond 3 time zones during study, patients being treated with sleep medication (e.g. anxiolytics, antihistamines, benzodiazepines) for less than 3 months or when suspension or dose modification of this drugs is being planned during the study course.

Design and carving of wooden prisms: 124 prisms of withered pine tree wood with dimensions 20x18x18 cm will be carved from 9 logs of 300x20x20 cm at Aserrío San Ignacio Ltda. production plant, located in Soacha, Cundinamarca. Given it is an industrial process of chainsaw cutting and wood planning, a quality control will be implemented consisting of verification of prism stability while lying on the floor, and the mean height in millimeters of every prism will also be measured and registered. Unsteady products or those with atypical mean heights, defined as a height either exceeding percentile 75 + 1,5 times interquartile range or below percentile 25 - 1,5 times interquartile range, will be discarded and not used during the study. As shown in figure 3, this non-pharmacological intervention was designed to obtain an inclination range dependent on the bed length of each patient (usually 1,90 cm in local industry). After exclusion of defective prisms, n groups of wooden prism pairs according to mean height in millimeters will be formed and every group will be given a random digit generated by computer. Afterwards, every random digit of prism groups will be sequentially assigned to a consecutive HBE-allocated patient number, in such a way that every consecutive patient number (among those allocated to HBE) will be linked randomly to a preset known prism height. This additional randomization procedure, involving prisms according to their mean height, is planned due to the impossibility to guarantee that prism height will be identical with a precision of ±1 mm, keeping in mind that products will be cut with chainsaw and will be planed as part of an industrial process.

	Improved with treatment B					
Improved with treatment A	No	Yes	Total			
No	r	S	r+s			
Yes	t	u	t+u			
Total	r+t	s+t	N pairs			

Discordant pairs =
$$\frac{s+t}{N \ pairs}$$
 = 53,8% $OR = \frac{s}{t} = 3,57$

	Improved without HBE					
Improved with HBE	No	Yes	Total			
No	29,4%	11,8%	41,2%			
Yes	42%	16,8%	58,8%			
Total	71,4%	28,6%	100%			

Figure 2: Matrices for sample size calculation, according to reference 20 and 26. HBE: Head of Bed Elevation.

In figure 4, a quality control graph is shown. Mean wooden prism height was a non-normal variable when Shapiro-Wilk test was applied (W: 0,908; critical W: 0,979; p: 0.000000). After using predefined exclusion rules for atypical values, 2 pairs of wooden prisms were discarded.

[figure not shown]

Figure 3: Schematic representation of HBE and expected bed inclinations.

Randomization: A list of 42 numbers will be generated, with subsequent binomial transformation, by using STATA 13.0 software for Windows (StataCorp LP, Texas, USA) in order to allocate participants in a 1:1 proportion to each one of the study arms. Wooden prisms will be marked with a consecutive number from 1 to 42 and they will be stored, keeping the marked number out of reach from the sight of the researcher in charge of patient recruiting.

Patients that meet the inclusion criteria, have no exclusion criteria and who give written informed consent, will be assigned a consecutive number during their outpatient visit according to their order of inclusion in the trial. These participants will be randomized to either HBE or control group in the moment that a member of the research team verifies, among the stored prisms, the existence of a prism pair marked with the same number as the consecutive number assigned to the patient. In the case that this pair does exist, then the patient will take home that pair of wooden prisms and use them during the first period of the trial according to spoken and written instructions to be given at that moment. On the contrary, if a pair of wooden prisms marked with the same consecutive number as the patient, does not exist, then it will be understood that the study participant has been allocated to control group during the first period of the trial. The member of the research team who verifies the storehouse of wooden prisms will not be in charge of confirming inclusion and exclusion criteria and will not assign consecutive numbers to patients during outpatient visits.

Allocation concealment: The researcher in charge of confirming inclusion and exclusion criteria, fulfilling the Basic Data Formulary and providing the patient with the Informed Consent Format, will not be aware of the allocation sequence order until these 3 documents have been applied to the participant and a consecutive number has been generated according to their order of inclusion in the trial. After that, a member of the research team in the prism storehouse will verify the existence of a prism pair marked with the same number as the consecutive number assigned to the patient, and only in that point allocation status of the participant will be known.

[figure not shown]

Figure 4: Wooden prisms quality control. ICR: Interquartile range; Q1: Quartile 1; Q3: Quartile 3.

Cross-over: After allocation has been completed, patients in the intervention group will receive a pair of numbered wooden prisms with dimensions 20x18x18 cm along with written instructions about the correct use of the intervention. The patient must sleep with HBE during 6 weeks and both RDQ and SF-36 questionnaires will be applied again at the end of this first period while the participant is still sleeping with HBE. Afterwards, a washout 2 week period follows in which the participant sleeping with HBE will stop using it and will return the pair of wooden prisms to the researchers. After washout period has ended and both RDQ and SF-36 questionnaires have been applied again, patients allocated to the control group during the first period of the study will receive a random pair of prisms and will be instructed to use the prisms for sleeping with HBE during a second period of 6 weeks. Meanwhile, participants initially allocated to the HBE group will be followed as a control group in this second period of the study.

Blinding: Because HBE is not susceptible to double-blinding, patients allocated to the intervention group will always be aware of the group they belong to. However, the researcher in charge of statistical analysis of data and writing the results report will work with random-generated alphabetical group codes for masking the intervention in each one of the periods of the trial.

Follow-up: After participant allocation, telephonic follow up will be made during both periods of the trial with a frequency that is dependent on the intervention group of the patient in that period. Participants in the HBE group will be called weekly for 2 weeks, and then will be called biweekly for a month, until each period of 6 weeks has ended. In contrast, patients in the control group will be called every three weeks along each period. With the purpose of verifying both HBE adherence and correct use of wooden prisms, every participant will be asked to send a photograph of the bed head legs during the follow-up telephone call. The photograph will be received by the researcher via e-mail or smartphone and will be encoded and saved in a hard disk. At the end of the first period, RDQ and SF-36 questionnaires will be applied and researchers will store the returned prisms during washout period. When washout period has ended, RDQ and SF-36 questionnaires will be applied again in order to be sure of the absence of any carry-over effect in the group initially allocated to HBE. Finally at week 14, RDQ, SF-36 and Patient Preference questionnaires will be administered to complete study ending outcome assessments.

In figure 5, a schematic representation of follow-up is shown.

[figure not shown]

Figure 5: Schematic representation of photographic and telephonic follow-up. W1-6: Weeks from 1st to 6th in each period.

Primary outcome:

1. Effectiveness: Change of ≥ 0,6 points between basal RDQ questionnaire and the same questionnaire administered after 6 weeks of HBE use.

Secondary outcomes:

- 1. Quality of life: Change of ≥ 10 percentage points between basal SF-36 questionnaire and the same questionnaire administered after 6 weeks of HBE use.
- **2. Patient preference:** Proportion of patients who preferred HBE, after finishing 14 weeks of the study.
- 3. Safety: Proportion of patients with any reported adverse event during HBE or without bed inclination.

Statistic analysis plan: Quantitative and qualitative variables collected with Basic Data Format, RDQ, SF-36 and Patient Preference questionnaires will be typed in a Microsoft Excel 2007 database. Intervention groups will be masked with an alphabetical code provided by an independent collaborator who will not be involved with data analysis or report writing. For statistical processing, database will be imported into STATA SE 13.0 for Windows (StataCorp LP, Texas, USA) and descriptive statistics will be generated for each variable. Statistically significant differences will be searched for categorical data using the Chi-square test or Fisher exact test and normality will be tested for numerical continuous variables using the Shapiro-Wilk test. For normally distributed continuous variables, statistically significant differences will be searched for by using unpaired Student's t test. Alternatively, for not normally distributed variables Mann-Whitney U test will be applied. For non-normal variables due to atypical data, values outside the percentile 50 ± 1,5 interquartile range were excluded. For complementary processing of primary outcome and secondary outcome quality of life, score difference

between periods will be transformed into a binomial variable and a McNemar marginal homogeneity test will be applied. McNemar mid-p was used if discordant pairs sum was smaller than 25²⁸. Differences with one-tail p<0,05 will be accepted as statistically significant. Exploratory subgroup analysis will search for differences stratified according to age group, sex, ethnic group, BMI, comorbidities, cups of coffee per day, pharmacological adherence, and length and severity of symptoms; among other 16 baseline variables. Subgroup interactions will be tested with Chi-square or Fisher exact test, and effect size was expressed as a univariate relative risk from a generalized linear model of binomial family. As part of internal quality control of the clinical trial, a pre-test was applied to prove the assumption of a negligible *carry-over* effect, according to expert guidelines²⁹. Analysis of variance (ANOVA) for crossover studies was used in search for significant sequence, period and treatment effects, assuming a negligible *carry-over* effect. In the modified intention to treat analysis, participants with protocol violations because of bad adherence to HBE, were included, but it was not possible to include patients who withdrew from the study because outcome information could not be gathered completely.

Methodology diagram: A schematic representation of the trial methodology is presented in figure 6.

[figure not shown]

Figure 6: Schematic representation of the trial methodology. RDQ: Reflux Disease Questionnaire; SF-36: Short Form 36 Questionnaire; HBE: Head of Bed Elevation; Standard treatment: Based on proton pump inhibitors and/or sodium alginate, according to treating physician criteria.

WORK TEAM

Work team of this clinical trial is formed by three authors. The respective roles during the design and conduction of the trial, and also the professional profiles of each researcher are described below.

Researchers:

- [name] (Principal Researcher study design, patient recruiting, telephonic follow-up, outcome assessment, statistical analysis, writing of final report)
 - General Practice Physician Universidad Nacional de Colombia
 - 3rd year Internal Medicine resident Universidad Nacional de Colombia
- [name](Researcher patient recruiting, intervention administration, clinical and telephonic follow-up, writing of final report)
 - General Practice Physician Universidad Nacional de Colombia

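### Specific objective 2 compares the groups in both periods and no analysis is named as deciding, so the plan can be followed with underpowered unpaired tests in each period

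*Combined protocol and SAP*

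**What the plan says.** Specific objective 2, the only specific objective that states an efficacy comparison, compares symptom severity and quality of life "among participants allocated to the HBE and the control group, in both the first and second period of study". The Cross-over section uses the same group language: "participants initially allocated to the HBE group will be followed as a control group in this second period of the study".

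The Sample size section sets one null and one one-sided alternative hypothesis for RDQ and one pair for SF-36. Each contrasts HBE with no HBE overall, without reference to period. The first calculation there is for a paired t test, which the section says is described in the statistical analysis section.

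The Statistic analysis plan contains no paired t test. For comparing continuous variables it lists the unpaired t test, or Mann-Whitney U if the data are not normal, without tying either to an endpoint or a period. It then adds two analyses that use both periods:
- a McNemar test on the dichotomised score difference between periods, for RDQ and SF-36, described as complementary;
- a cross-over ANOVA for sequence, period and treatment effects.

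The significance rule covers every test: "Differences with one-tail p<0,05 will be accepted as statistically significant". Nothing says which analysis decides an endpoint, or what standing by-period results have.

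**The concern.** A cross-over gains its precision from comparing each patient with himself or herself. An unpaired comparison of HBE and control within one period treats the trial as a small parallel-group study and gives up that gain. Objective 2 read together with the unpaired tests leads an analyst to exactly that, once in each period, for each endpoint.

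Two things are at stake. First, power: the sample size rests on paired analyses, so the planned number does not support by-period tests. Second, interpretation: with period 1, period 2, McNemar and ANOVA results all available at the same threshold and none ranked, a favourable one could be presented as the trial's answer, and the plan does not say how to conclude when they differ.

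**Working it through.** **Inputs.** From Sample size: "an RDQ mean and standard deviation of 3,3±1,0"; "an SF-36 mean and standard deviation of 56,9±20,3"; target differences of "0,6 points in RDQ questionnaire (range: 1 to 6) and 10 points in SF-36 questionnaire (range: 0 to 100"); "Effect size (Cohen d) was calculated as 0,49"; "maintaining a statistical power of 80%, required sample size was adjusted to a total of 34 patients"; final enrolment 42. Hence 34/2 = 17 evaluable or 42/2 = 21 enrolled patients per sequence. Alpha is one-tail 0.05. The within-patient correlation ρ is not stated, so 0, 0.5 and 0.7 are assumed. Equal SDs, equal correlation between visits, and no period or carry-over effect are also assumed.

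**The plan's own figures reproduce.**
- Paired t: dz = 10/20.3 = 0.4926. With N = 27 the noncentrality is 0.4926 × √27 = 2.560, critical t (26 df) is 1.706 and power is 0.8016, as stated.
- McNemar: 34 × 0.53782 = 18.3, so 18 discordant pairs. P(X ≥ 13) is 0.0481 at probability 0.5 and 0.8169 at 3.571/4.571, as stated.
- Both calculations use each patient's two conditions. Using 20.3 as the SD of differences implies ρ = 0.5, because 20.3 × √(2(1 − 0.5)) = 20.3.

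**False positives if either period counted.** The chance is 0.05 + 0.05 − P(both significant). With independent results this is 0.10 − 0.0025 = 9.75%. On end-of-period scores the two contrasts have correlation −ρ, so P(both) falls to 0.0001 at ρ = 0.5 and the total reaches 10.0%.

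**Power of one period, unpaired t, RDQ effect 0.6, end-of-period scores.** d = 0.6/1.0 = 0.6; noncentrality = d√(n/2).
- n = 17: 0.6 × √8.5 = 1.749, power 52.7%.
- n = 21: 0.6 × √10.5 = 1.944, power 60.5%.

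**Same test on change scores.** The SD becomes √(2(1 − ρ)): 1.414, 1.0 and 0.775 at ρ = 0, 0.5 and 0.7. So d = 0.424, 0.600 and 0.775. Power is 33%, 53% and 71% (n = 17) or 38%, 61% and 79% (n = 21).

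**Pooled within-patient contrast, end-of-period scores.** Compare the period 1 minus period 2 difference between sequences. The mean contrast is 2 × 0.6 = 1.2, the SD is √(2(1 − ρ)), and the noncentrality is (1.2/SD) × √(n/2).
- n = 17: 2.47, 3.50 and 4.52, giving power 78%, 96% and over 99%.
- n = 21: 2.75, 3.89 and 5.02, giving 85%, 98.5% and over 99%.

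A common baseline cancels from this contrast and leaves these figures unchanged. With change from each period's own starting score, the SD is 2√(1 − ρ), so 1.2/SD = 0.600, 0.849 and 1.095. Power is then 53%, 78% and 93% (n = 17) or 61%, 85% and 97% (n = 21). That is lower, but still above the by-period power on the same score.

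**Agreement between periods** (simulation, 40,000 trials per scenario, effect 0.6; values for 17 / 21 per sequence):

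| Score analysed | ρ | Both periods significant, % | Exactly one significant, % |
|---|---|---|---|
| End of period | 0 | 28 / 37 | 50 / 48 |
| End of period | 0.5 | 20 / 30 | 65 / 62 |
| End of period | 0.7 | 17 / 27 | 72 / 68 |
| Change, own-period baseline | 0 | 11 / 15 | 44 / 47 |
| Change, own-period baseline | 0.5 | 28 / 37 | 50 / 47 |
| Change, own-period baseline | 0.7 | 51 / 63 | 41 / 33 |
| Change, common baseline | 0 | 5 / 8 | 57 / 61 |
| Change, common baseline | 0.5 | 20 / 30 | 65 / 62 |
| Change, common baseline | 0.7 | 46 / 60 | 51 / 39 |

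**SF-36** (d = 10/20.3 = 0.49, end-of-period scores): by-period power is 41% / 47%. Pooled power is 63% / 72% at ρ = 0, 88% / 93% at 0.5 and 98% / 99% at 0.7.

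**The case against.** The best defence is that the plan already tests the right thing. Its hypotheses carry no period index, the sample size uses paired methods, and McNemar and the cross-over ANOVA both pool the periods. Objective 2 can be read as describing use of data from both periods, which is how any cross-over is described, and the objectives beside it are operational. The unpaired tests are tied to no endpoint and might be meant for baseline comparisons. By-period reporting is ordinary and harms only if it decides the conclusion.

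Much of this stands, and it rules out three stronger readings:
- A reader might infer that the plan has no means of combining the periods. It has: the ANOVA and McNemar do so.
- A reader might infer that the plan runs at a 10% error rate. Objective 2 does not say the periods are tested separately, and nothing says that one significant period is enough. The 10% is conditional on a rule the plan does not state.
- A reader might infer that one significant and one non-significant period is always the likeliest result when HBE works. That depends on the score. The primary outcome is worded as a change from baseline; on change from each period's own baseline at ρ = 0.7, both periods are significant more often than exactly one.

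The defence does not supply a deciding analysis. McNemar is complementary by the plan's own label, which suggests that the tests listed before it are the main ones, and those are unpaired. The ANOVA is described as a search for three kinds of effect and is not linked to objective 2 or to the primary outcome.

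**Conclusion.** The point holds as a gap in specification. The objective, the hypotheses, the sample size and the listed tests do not name the same analysis, and none is designated as deciding. Following the text can therefore produce two unpaired tests per endpoint, each with 33% to just under 80% power for a 0.6-point RDQ effect, depending on score form, correlation and number per sequence. On end-of-period scores the like-for-like comparison is 53% to 60% by period against 78% to 85% pooled at correlation 0 and at least 96% at 0.5 to 0.7. Disagreement between periods ranges from 33% to 72%.

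These figures rest on the SDs quoted in Sample size, on assumed correlations, and on no period or carry-over effect. The appropriate analysis is already in the plan; what is missing is its status.

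**What to change.** Reword specific objective 2 and the Statistic analysis plan so that each endpoint (RDQ primary, SF-36 secondary) has one deciding test: the within-patient HBE versus no-HBE treatment effect from the planned cross-over ANOVA, with period in the model. State which score enters the model, since end-of-period scores and change from each period's own baseline differ in precision. Keep McNemar as complementary, say what the unpaired tests are for, and correct the Sample size reference to a paired t test that the analysis section does not contain. Add that by-period comparisons are descriptive and can neither support nor overturn the conclusion.

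The cost is a few sentences, with no new data or patients. The downside is that by-period p-values lose confirmatory status.
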